4.1.1 Presentation of results in summary tables

If not stated otherwise, tabulations will be presented by treatment group as follows:

- Olaparib 300 mg bid
- Placebo bid
- Total

Data listings will include at least the following details:

- Patient identifier
- Centre identifier
- Actual / randomised treatment group

Data listings will be sorted by treatment group (planned or actual) and patient ID, if not stated otherwise.

4.2 Analysis Methods

A single interim PFS analysis for futility will be performed when 50% of the final number of progression events has been reached (approximately 44 PFS events). A final PFS analysis will be performed when approximately 87 progression events have occurred (60% maturity) (DCO1). No further analyses of PFS are planned beyond this point.

One interim analysis for OS will be performed at the time of the final PFS analysis (approximately 87 PFS events). A final formal analysis of OS will be performed when approximate 106 death events have occurred (DCO2). **CCI**

Individual efficacy response data will be listed in a by-patient listing.

A summary of the outcome variables to be analysed at each DCO is shown in [Table 10](#) below.

Table 10 **Timing of Statistical Analyses**

Timing of analysis	Outcome Variable
Interim PFS when ~44 PFS events reported	PFS
Final PFS when ~87 PFS events reported (DCO1)	PFS, PFS2, TDT, TFST, TSST, OS, ORR, BoR, DoR and adjusted mean change from baseline in global HRQoL score.
Final formal OS when ~106 OS events reported (DCO2)	OS, PFS (investigator assessment), PFS2, TDT, TFST, TSST, and adjusted mean change from baseline in global HRQoL score.
CCI	

Safety variables will be analysed at each analysis time point.

There will be no further analyses done unless requested by health authorities.

The treatment comparison is olaparib 300 mg bid versus placebo.

The following table details which efficacy endpoints are to be subject to formal statistical analysis, together with pre-planned sensitivity analyses making clear which analysis is regarded as primary for that endpoint.

Table 11 **Formal Statistical Analyses to be Conducted and Pre-Planned Sensitivity Analyses**

Endpoints Analysed	Notes
PFS	Primary analysis: log-rank test using BICR data
	Key sensitivity analyses: log-rank test using BICR data in randomised patients confirmed as gBRCA mutation positive by the Myriad test (if subset of FAS)
	Additional sensitivity analyses:
	1) Evaluation time bias analysis; log-rank test using BICR data
	2) Attrition bias analysis (using alternative censoring rules); log-rank test using BICR data
	3) Ascertainment bias analysis; log-rank test using investigator data

Table 11 Formal Statistical Analyses to be Conducted and Pre-Planned Sensitivity Analyses

Endpoints Analysed	Notes
	4) Deviation bias analysis (if meaningful to do); log-rank test using BICR data
OS	Primary analysis: log-rank test
	Key sensitivity analysis: log-rank test data in randomised patients confirmed as gBRCA mutation positive by the Myriad test (if subset of FAS)
	Supportive analysis: Kaplan-Meier (KM) plot of time to censoring for OS
PFS2	Primary analysis: log-rank test using investigator assessment of second progression
	Key sensitivity analysis: log-rank test in randomised patients confirmed as gBRCA mutation positive by the Myriad test (if subset of FAS)
TDT	Primary analysis: log-rank test
	Key sensitivity analysis: log-rank test in randomised patients confirmed as gBRCA mutation positive by the Myriad test (if subset of FAS)
TFST	Primary analysis: log-rank test
	Key sensitivity analysis: log-rank test in randomised patients confirmed as gBRCA mutation positive by the Myriad test (if subset of FAS)
TSST	Primary analysis: log-rank test
	Key sensitivity analysis: log-rank test in randomised patients confirmed as gBRCA mutation positive by the Myriad test (if subset of FAS)
ORR	Primary analysis: logistic regression using BICR data
	Sensitivity analysis: logistic regression using investigator data
Adjusted mean change from baseline in global HRQoL score	Primary analysis: mixed model for repeated measures (MMRM) analysis of all of the post-baseline scores for each visit CCI [REDACTED]
Time to sustained clinically meaningful deterioration in HRQoL	Primary analysis: log-rank test Supportive analysis: attrition bias analysis (log-rank test using alternative censoring rules)

4.2.1 Multiplicity

In order to describe the nature of the benefits of olaparib maintenance treatment, PFS and OS will be tested at a 1-sided significance level of 2.5%.

In addition to these planned analyses, which will be performed and reported in the CSR, in order to strongly control the type I error at 2.5% 1-sided for key label claims, a multiple testing procedure (MTP) will be employed across the primary endpoint (PFS) and key secondary endpoint (OS).

A hierarchical testing strategy will be employed where PFS is tested first using the full test mass (full test mass = alpha 2.5% 1-sided) and the key secondary endpoint of OS will then be tested using a MTP with a recycling strategy (ie, the MTP will recycle the test mass to the endpoint not yet rejected in the hierarchy outlined in [Figure 2](#)).

The MTP is detailed below.

Figure 2 Multiple Testing Procedure

The OS will only be tested if the null hypothesis (of no difference) is rejected for PFS. One interim analysis for OS will be performed at the time of the final PFS analysis (approximately 87 PFS events) (DCO1). A final formal analysis of OS will be performed when approximately 106 death events have occurred (DCO2). CCI

The Lan and DeMets approach that approximates the O'Brien & Fleming spending function will be employed to preserve the overall 1-sided type-I error rate of 2.5% ([Lan and DeMets 1983](#)). If the interim analysis for OS occurs at exactly 57% of the 106 OS events (60 OS events), statistical significance for OS will be declared if the null hypothesis for PFS is rejected and the observed p-value for OS is $p < 0.003$, which equates to a $HR \leq 0.49$. The significance level at the interim (DCO1) and the final formal analysis (DCO2) of OS will be determined based on the observed number of events at the time of the interim and the planned number of events at the final analyses. This will be documented in the minutes of the blind data review meeting prior to DB lock at DCO1. If the interim analysis for OS (DCO1) occurs at exactly 57% of OS events and the number of OS events at the final formal OS analysis is approximately 106 then the 1-sided significance level to be applied for the final formal OS analysis will be 2.4%. Statistical significance for OS would be declared if the observed p-value for OS is $p < 0.024$, which equates to a $HR \leq 0.68$. This plan was further revised as below.

DCO1 took place on 15th Jan 2019 at which time details of the alpha spending plan were updated. Based on the observed 71 OS events at the interim analysis, i.e. 67% of the 106 OS

events which are planned for the final analysis, statistical significance for OS was to be declared if the null hypothesis for progression-free survival (PFS) was rejected and the observed one-sided p-value for OS was $p < 0.006$. Also, given that the number of OS events at the final analysis is planned as 106 the one-sided significance level to be applied for the final analysis will be $p < 0.023$.

4.2.2 Primary variable - progression free survival

A summary of PFS will be prepared to present the number of patients with progression and no progression. Tabulation will detail the total number of progressions and no progressions, the number of patients with progression identified by RECIST (separately for TLs, NTLs, and new lesions) and death as well as details about non-progressed patients including the number of patients progression-free at time of DCO, lost to follow-up, withdrawn consent, and prematurely censored (RECIST or death) if they did not progress and if the latest scan prior to DCO was more than one scheduled tumour assessment interval (+ 2 weeks) prior to the DCO date. The summary will be presented by treatment group.

The PFS as defined in Section 3.2.1 will be analysed using a log-rank test for generation of the p-value and using the Breslow approach for handling ties in the following manner:

CCI
[Redacted]

By using the TEST-Statement within LIFETEST procedure the test statistics U and the covariance matrix will be averaged over the possible orderings of the tied failure times (SAS Lifetest 2008).

The HR and its CI will be estimated from the log-rank (U and V statistics) follows directly from the LIFETEST model as used above for calculation of p-values (Berry et al 1999 and Sellke et al 1983)

CCI
[Redacted]

CCI
[Redacted]

The log-rank test statistic, the HR (olaparib vs. placebo) together with its corresponding 95% CI and p-value will be presented (a HR less than 1 will favour olaparib).

The median and 95%-CI of PFS and the proportion of patients progression-free at 6 months, 12 months, 18 months, 24 months, 36 months and 48 months will be summarised and presented by treatment group. Further timepoints will be added as appropriate.

In addition, duration of follow-up will be summarised using median time from randomisation to date of censoring (date last known to be non-progressor) in censored (not progressed) patients only, presented by treatment group.

The following KM plots of PFS will be presented by treatment group. The KM plot will be prepared using LIFETEST procedure and selecting ODS graphics. The plot will identify censored patients using a different symbol and include patients at risk at specific time points:

- PFS
- PFS with censoring and event flags reversed

The assumption of proportionality will be assessed. The results of these model checks will not be presented in the CSR as part of the formal outputs; however, any deviation from this assumption will be considered in the interpretation. Note that in the presence of non-proportionality, the HR will be interpreted as an average HR over the observed extent of follow-up. Proportionality will be tested firstly by producing plots of complementary log-log (event times) versus log (time) and, if these raise concerns, a time dependent covariate would be fitted to assess the extent to which this represents random variation. The complementary log-log plot will be directly produced in SAS LIFETEST procedure using ODS graphics option PLOTS=(LLS) in the PROC-Statement. The graph will be assessed visually. Two parallel lines favour the proportionality assumption. To support the proportionality assessment a Cox proportional hazard's model will be constructed containing the interaction of treatment and the logarithm of PFS_time (treatment*log(PFS_time)). The p-value obtained from the Wald Chi-squared test for the time dependent covariate will be presented. The following SAS-code may be used:

CCI

A further analysis of PFS (using investigator assessed RECIST) was to be performed at the time of the final OS analyses, if requested by health authorities. A final decision was to be made at the BDRM for the final OS analysis. However, a decision was made after the analysis of PFS at DCO1 to carry out a full descriptive PFS analysis using investigator assessed RECIST at the time of the final OS analysis at DCO2. If patients are still on treatment at the time of DCO2 (i.e. investigator assessment of RECIST progression continues), then the analysis will be presented again at DCO3.

4.2.2.1 Progression-free survival sensitivity analyses

As a sensitivity analysis to the primary endpoint of PFS, the primary analysis will be repeated excluding any patients who did not have a gBRCA mutation status confirmed by the central Myriad test. The same methodology and model will be used as for the primary analysis and the HR and associated 95% CI will be reported. A KM plot of PFS in this subset of patients will be presented by treatment group.

a) Attrition bias

Attrition bias will be assessed by repeating the primary PFS analysis except that the actual PFS event times, rather than the censored times, of patients who progressed or died in the absence of progression immediately following two, or more, non-evaluable tumour assessments will be included. In addition, patients who take subsequent therapy prior to their last evaluable RECIST assessment or progression or death will be censored at their last evaluable assessment prior to taking the subsequent therapy.

A by-patient listing will be produced similar to the PFS listing but including only patients who progressed but were censored for the primary analysis due to missing of two, or more, non-evaluable tumour assessments. The actual PFS times will be reported.

(b) Evaluation-time bias

A sensitivity analysis will be performed to assess possible evaluation-time bias that may be introduced if scans are not performed at the protocol-scheduled time points. The log-rank test, as described for the primary analysis of PFS, will be repeated using the midpoint between the time of progression and the previous evaluable RECIST assessment to derive PFS time for patients with RECIST progression events. For patients whose death was treated as a PFS event, the date of death will be used to derive the PFS time used in the analysis. This approach has been shown to be robust to even highly asymmetric assessment schedules ([Chen and Sun 2010](#)). This approach will use the BICR RECIST assessments.

To support this analysis, the individual mean time difference between RECIST assessments (patient inter-assessment times) will be calculated and summarised using descriptive statistics.

[figure not shown]
(c) Ascertainment bias

The primary analysis of PFS (log-rank test) will be repeated using investigator assessed RECIST data. The HR and 95% CI will be presented. A KM plot of PFS based on the investigator assessed RECIST data will be presented by treatment group.

Ascertainment bias will be assessed through the use of two measures proposed by Amit ([Amit, et al., 2011](#)): the early discrepancy rate (EDR) and late discrepancy rate (LDR). The EDR represents the positive predictive value of Investigator assessment and quantifies the frequency with which the Investigators declare progression early relative to BICR within each arm as a proportion of the total number of Investigator assessed PD's. The LDR quantifies the frequency that the Investigators declare progression later than BICR as a proportion of the

total number of discrepancies within the arm. If the distribution of discrepancies is similar between the arms, then this suggests the absence of evaluation bias favouring a particular arm.

EDR and LDR are calculated as:

The EDR and LDR will be calculated for each treatment arm and the differential discordance around each measure will be defined as the rate on the experimental arm minus the rate on the control arm.

If there is an important discrepancy between the primary analysis using BICR assessments and this sensitivity analysis using investigator assessments, the proportion of patients with site but no central confirmation of progression will be summarised by treatment group and the primary analysis will be repeated for this subset of patients. The approach of imputing an event at the next visit in the central review analysis may help inform the most likely HR value, but only if an important discrepancy exists. Discrepancy between the primary analysis using BICR assessments and investigator assessments of progression will be discussed at the BDRM. The study team will decide whether the discrepancy between assessments is of importance and whether or not additional analyses are required.

A by-patient listing will be produced to present patients where at least one assessment differs between investigator and central reviews of RECIST progression.

(d) Deviation bias

As a sensitivity analysis to the primary endpoint of PFS, an analysis excluding patients with “important” deviations that may affect the efficacy of the trial therapy will be performed if the following deviations were reported for > 10% of patients:

- did not have the intended disease or indication or
- did not receive any randomised therapy

A log-rank test will be repeated using the BICR RECIST data, using the same method as described for the primary analysis of PFS. The HR and 95% CI will be presented.

The treatment status at progression by patients who have progressed / censored including the number of patients and percentage of on-treatment or discontinued will be tabulated. The number of days from treatment discontinuation to progression for patients who have discontinued treatment will be summarised descriptively. Data will be presented by treatment group.

Patients censored for progression at more than 14 weeks before the DCO ('censored > 14 weeks before DCO', 'censored <= 14 weeks before DCO') will be tabulated and presented by treatment group.

A by-patient listing will be produced including patients with an important deviation only.

4.2.2.2 Progression-free survival subgroup analyses

Subgroup analyses will be conducted comparing PFS between treatments. The purpose of the subgroup analyses is to assess the consistency of treatment effect across potential or expected prognostic factors. KM plots will be produced for each subgroup according to treatment group.

If there are too few events available for a meaningful analysis of a particular subgroup (it is not considered appropriate to present analyses where there are less than 5 events in a subgroup in at least one treatment group), the results of the subgroup analysis (HR and 95% CI) will not be presented, however, all patients with non-missing subgroup data will be included in the Cox model used for the analysis (see below).

The following subgroups will be analysed for PFS:

- Previous chemotherapy (FOLFORINOX variants, gemcitabine/cisplatin, other); Reference=FOLFORINOX variants
- Type of previous chemotherapy (doublets, triplets, other); Reference=doublets
- Time on first-line treatment till randomisation (≤ 6 months vs > 6 months); Reference= ≤ 6 months
- Best response on first-line treatment (SD vs PR/CR); Reference=SD

These will be determined from the "Metastatic Pancreas Cancer Therapy" (CAPRX2) module of the eCRF at screening by medical review.

- Presence or absence of biliary stent; Reference=Presence of biliary stent

This will be determined from the "Surgical History" (HISS) module of the eCRF at screening by medical review.

- Measurable versus non measurable disease / NED at baseline; Reference=non measurable disease / NED at baseline

This will be determined programmatically from the baseline BICR results.

- gBRCA mutation type (BRCA1, BRCA2, BRCA1/2 (both), non-gBRCAm); Reference=BRCA1

This will be determined programmatically from the Myriad central laboratory test results.

- Age at randomisation (≥ 65 vs < 65); Reference= < 65
- Race (White vs Other); Reference=White
- Sex (Male vs Female); Reference=Male

These will be determined programmatically from the “Demography” (DEM) module of the eCRF at screening.

- ECOG performance status (normal activity, restricted activity); Reference=normal activity

The data will be determined from the “ECOG Performance Status” (PSTAT) module of the eCRF at screening.

Other baseline variables may also be assessed if there is clinical justification. A final decision will be made at the BDRM.

For each subgroup, the HRs (olaparib: placebo) and associated CIs will be calculated from a Cox proportional hazards model (TIES = Efron) that contains the treatment group, factor (subgroup) and treatment-by-factor interaction term. All patients with non-missing subgroup category data will be included in the Cox model. Statistics produced by the Cox model, i.e. HR/CI will only be displayed in subgroup categories with a sufficient number of events available (at least 5 events in both treatment groups), otherwise, only the total number of patients and events will be displayed. Reference cell coding will be used introduced by the PARAM=REFERENCE option in the CLASS-Statement. Individual reference levels will be defined using the REF= option within the CLASS-Statement for each subgroup. The treatment effect HRs for each treatment comparison along with their CIs will be obtained for each level of the subgroup from this single model. Analysis will be carried out using PHREG procedure in SAS in the following manner:

CCI [REDACTED]

The HRs and 95% CIs will be presented in an overview table as well as on a forest plot including the HR and 95% CI from the overall population (using the HR and 95% CIs from the primary analysis).

CCI

The presence of quantitative interactions will be assessed by means of an overall global interaction test. This will be performed in the overall population by comparing the fit of a Cox proportional hazards model including treatment, all covariates, and all covariate-by-treatment interaction terms, with one that excludes the interaction terms and will be assessed at the two-sided 10% significance level. If a covariate does not have more than 5 events per level in both treatment groups (of the covariate) it will be included as a covariate in the model but the covariate-by-treatment interaction term will be omitted. If the fit of the model is not significantly improved then it will be concluded that overall the treatment effect is consistent across the subgroups.

If the global interaction test is found to be statistically significant, an attempt to determine the cause and type of interaction will be made. Stepwise backwards selection will be performed on the saturated model, whereby (using a 10% level throughout) the least significant interaction terms are removed one-by-one and any newly significant interactions re-included until a final model is reached where all included interactions are significant and all excluded interactions are non-significant. Throughout this process all main effects will be included in the model regardless of whether the corresponding interaction term is still present. This approach will identify the factors that independently alter the treatment effect and prevent identification of multiple correlated interactions.

Any quantitative interactions identified using this procedure will then be tested to rule out any qualitative interaction using the approach of [Gail and Simon 1985](#).

For all subgroups, median PFS time and 95% confidence intervals calculated using the Kaplan Meier method will be summarised by treatment group.

In order to assess the impact of imbalances between treatment groups in terms of the key prognostic variables best response on first-line treatment (CR/PR, SD), time on first-line treatment (≤ 6 months, > 6 months), age group (< 65 years, ≥ 65 years), ECOG status at baseline (0 normal activity, 1 restricted activity), and previous chemotherapy (FOLFORINOX variants, Gemcitabine/Cisplatin, Other), a Cox proportional hazards model including only treatment group will be compared with a Cox proportional hazards model including treatment group and key prognostic variables. The hazard ratio for treatment group and 95% confidence intervals will be presented.

A by-patient listing will be produced for presenting individual PFS data.

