4.2.3 Overall Survival

A summary of survival status at the time of analysis will be produced. This will summarise the number of patients who have died, who are still in survival follow-up, who are lost to follow-up or who have withdrawn consent. Results will be presented by treatment group.

Interim OS data as defined in Section 3.2.2 will be analysed at the time of the final analysis for PFS (DCO1) and will use the same methodology and model (provided there are sufficient events available for a meaningful analysis [> 5 deaths in both treatment groups], if not descriptive summaries only will be provided). A final formal analysis of OS will be performed when approximately 106 deaths have occurred (DCO2). CCI

Median OS time and corresponding 95% CI will be summarised including the number of deaths, and survival at month 6, 12, 18, 24, 36 and 48. Further timepoints will be added as appropriate. Results will be presented by treatment group.

The analysis will be repeated excluding any patients who did not have a gBRCA mutation status confirmed by the central Myriad test.

The sensitivity analyses outlined for PFS in Section 4.2.2 will not be repeated for OS with the exception of a KM plot. Two KM plots will be produced. The first KM plot will show time to censoring of OS and the second KM plot will show time to censoring where the censoring indicator is reversed (median time to follow-up where events will be censored and previously censored patients will be treated as events). The first KM plot will be repeated excluding any patients who did not have a gBRCA mutation status confirmed by the central Myriad test.

OS data will be listed in a by-patient listing.

Similar subgroup analyses (except the interaction test) will be conducted comparing OS between treatments as detailed for PFS in Section 4.2.2.2, using the same methodology and model. KM plots will be produced for each subgroup according to treatment group. If there are too few events available for a meaningful analysis of a particular subgroup (it is not considered appropriate to present analyses where there are less than 5 events in a subgroup in at least one treatment group), the relationship between that subgroup and OS will not be formally analysed. In this case, only descriptive summaries (number of patients, number (%) of events, and KM plots) will be provided.

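### The global PFS interaction test (SAP 4.2.2.2) does not hold its stated 10% level and has too little power for non-rejection to be reported as consistency

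*SAP*

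**What the plan says.** Section 4.2.2.2 gives the aim: "The purpose of the subgroup analyses is to assess the consistency of treatment effect" across prognostic factors. It lists eleven factors: eight binary, two with three levels and one with four. Subgroup estimates are shown directly: "The HRs and 95% CIs will be presented in an overview table as well as on a forest plot".

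One global test then compares two nested Cox models, with and without all the interactions, and sets the full model against the reduced one, "with one that excludes the interaction terms and will be assessed at the two-sided 10% significance level". A sparse-level rule applies: "If a covariate does not have more than 5 events per level in both treatment groups", the interaction is dropped but the main effect stays.

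Both outcomes have a prescribed reading:
- Without a significant improvement in fit, "then it will be concluded that overall the treatment effect is consistent across the subgroups".
- With one, a stepwise search follows in which the weakest interactions "are removed one-by-one and any newly significant interactions re-included until a final model is reached". The SAP says of it: "This approach will identify the factors that independently alter the treatment effect".

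Section 4.2.3 leaves the test out for survival: "Similar subgroup analyses (except the interaction test) will be conducted comparing OS between treatments".

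The section names no test statistic, gives no small-sample reference and makes no statement about power. Nearby code is redacted, so its absence is not held against the plan.

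**The concern.** A likelihood-ratio statistic follows its chi-square reference only when there is ample information per parameter. Fitting more than twenty parameters to about 87 events is far from that, and the test can then reject too often. Separately, an omnibus test spread over 5-10 degrees of freedom has little power against an interaction in one factor. A rule that turns non-rejection into a finding of consistency then reads absence of evidence as evidence of absence.

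The two faults pull in opposite directions. Over-rejection makes the consistency conclusion harder to reach and low power makes it easier, so correcting the level alone would worsen the second fault. What is at stake is how the subgroup section is interpreted: this is its only rule that turns the subgroup results into an overall conclusion.

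**Working it through.** **Inputs from the SAP.** Section 1.3: about 145 patients at 3:2 (87 olaparib, 58 placebo), about 87 PFS events, HR 0.54, exponential PFS with a 4-month placebo median, 15 months of accrual. Section 4.2.2.2: eleven factors, Efron ties for the subgroup Cox models, the more-than-5-events rule, the 10% level.

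**The plan's own figure.** Events for 80% power at one-sided 2.5%: (1.960 + 0.842)² / [0.6 × 0.4 × (ln 0.54)²] = 7.849 / (0.24 × 0.3797) = 86.1, rounded up to 87. This reproduces the SAP; 87 events give 80.4% power.

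**Parameter count.** Full interaction df: 8×1 + 2×2 + 1×3 = 15. Main effects: the same 15 plus treatment, 16. After the rule, and after removing aliased terms, the simulated mean interaction df was 5.4 to 9.8 and the mean number of parameters 21.1 to 25.7.

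**Power by formula.** For a two-fold ratio of HRs in a 50/50 factor, the noncentrality is (ln 2)² × 87 × 0.24 × 0.25 = 0.4805 × 5.22 = 2.51. With a noncentral chi-square at a true 10% level, the miss rate is 70.7% (5 df), 73.7% (7 df), 75.8% (9 df) and 77.2% (11 df).

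**Simulation assumptions.** The SAP gives no prevalences, so three sets were assumed (sparse / intermediate / balanced):
- FOLFIRINOX variants, gemcitabine-cisplatin, other: 80-5-15 / 70-15-15 / 50-25-25%, with type of chemotherapy largely determined by regimen
- first-line time over 6 months: 35 / 45 / 50%
- PR/CR: 50% in all
- stent: 10 / 20 / 35%
- measurable disease: 85 / 75 / 60%
- BRCA1, BRCA2, both, none: 30-67-1-2 / 35-60-2-3 / 40-55-2-3%
- age 65 or over: 27 / 35 / 40%
- other race: 8 / 20 / 30%
- second sex level: 45 / 45 / 50%
- restricted ECOG: 30 / 40 / 50%

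Data were cut at the 87th event, the sparse-level rule was applied in each trial, and the likelihood ratio was referred to chi-square on the rank difference. The Cox log-likelihoods matched a standard package.

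**Level: rejection at nominal 10% with HR 0.54 in everyone (%)**

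| Run | Sparse | Intermediate | Balanced |
|---|---|---|---|
| Continuous times, 1000 trials | 16.9 | 19.6 | 24.8 |
| 8- then 12-week scan grid, 1000 trials | 16.4 | 20.3 | 25.4 |
| Separate program, 600 trials | 19.0 | 18.7 | 20.8 |
| Separate program, 500 trials | 16.2 | 17.8 | 24.2 |
| Separate program, 500 trials | 14.8 | 22.6 | 22.6 |

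The Monte Carlo SE is 1.2-1.4 points in the first two rows and 1.6 in the third. A further program with other prevalence sets gave 16-22%. Where other statistics were tried, a score test gave 16.8 / 19.0 / 24.4% and a joint Wald test 14.8 / 16.4 / 21.2%, so the excess is not peculiar to the likelihood ratio.

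With ten times the data (870 events, 11 df, balanced factors) rejection was 9.9% in 1200 trials, which points to a small-sample effect. A shorter run at that size with less balanced factors (300 trials, about 12 df) gave 14.0%, SE 2 points.

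**Power: two-fold ratio of HRs in one binary factor**
- Nominal cut-off, best response split 50/50 (600 trials each; continuous, grid): 37.5, 38.8 / 43.0, 41.0 / 38.0, 37.5% reject, so 57.0-62.5% miss.
- Other programs at the nominal cut-off, with factors at 40-50% prevalence: misses of 59-65% and 60-69%.
- Critical value adjusted to a true 10% level: 30.8, 28.7 / 24.8, 24.0 / 20.0, 18.8% reject, so 69-81% miss. Another program gave 75% and 77%, with the nominal p-value compared to 0.043 and 0.033.
- Larger interactions at the nominal cut-off: 56-63% reject at ratio 3 and 72-80% at ratio 4.

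**Stepwise step.** After a false global rejection the search kept at least one factor in 99.4-100% of trials (mean 1.9-2.7).

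**Bootstrap alternative.** Resampling from the fitted no-interaction model (400 trials, 79 resamples, continuous times) rejected 11.0 / 10.3 / 8.3% under the null. At a two-fold ratio it rejected 23.3 / 22.8 / 21.5%, against 37.3 / 37.0 / 41.0% for chi-square in the same trials. A cruder check put its null level at 8.7-14.4%.

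**The case against.** The strongest reply is that this is a supportive analysis with no confirmatory weight. It lies outside the PFS/OS testing procedure, is not run for OS, and changes no population or endpoint. The subgroup HRs, intervals and medians are displayed, so a reader can see the imprecision. Low power for interactions is common in a trial of 145 patients, and a 10% level is already more lenient than 5%. All of this stands and sets the severity. It does not defend a prescribed conclusion that the test cannot carry.

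The sizes also rest on assumed prevalences. That stands too: rejection near 25% appears only with fairly balanced factors, and the covariate list may be extended at the blind data review meeting. The direction was the same in every set tried.

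The stepwise result is largely what one expects when selection at 10% follows a significant joint test at 10%, and the SAP introduces the search as an attempt. It supports only a change of label.

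Three stronger readings are tempting but unsupported:
- That the primary PFS result or the overall type I error is affected. The interaction test plays no part in either.
- That a miss rate near 60% is a property of the plan. It holds for one binary factor that is about evenly split, and is worse with imbalance.
- That the SAP specifies a wrong reference distribution. It names none, and the nearby code is redacted.

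**Conclusion.** The point holds as a minor one. Under assumed prevalences and a chi-square likelihood-ratio reference, the nominal 10% test rejects in roughly 15-25% of trials with no interaction, an excess of about 5-15 percentage points. At that inflated level it misses a two-fold ratio of HRs in about 57-69% of trials when the factor is binary with 40-50% prevalence; at a true 10% level it misses about 70-80%. The low-power conclusion is the firmer of the two, since for an evenly split factor it follows from the event count and degrees of freedom alone. The inflation is firm in direction and approximate in size. A non-significant result therefore does not establish consistency, and a significant one is weaker evidence of heterogeneity than its nominal level suggests. Nothing here shows that the treatment effect does differ between subgroups.

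**What to change.** 1. In section 4.2.2.2, replace the consistency sentence with: *no evidence of heterogeneity was found; the test has low power and the subgroup HRs with 95% CIs are descriptive*.
2. State there that the nominal 10% level is approximate and anti-conservative at this number of events.
3. In the stepwise paragraph, say that the search *may suggest* factors rather than identifies them, and label any retained factor exploratory.

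A parametric-bootstrap p-value, with the sparse-level rule re-applied in each resample, is optional. It should be labelled supplementary, should not trigger the stepwise search, and should be given only together with change 1: it lowers rejection at a two-fold ratio to about 22-23% and is only approximately sized.

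The cost is SAP or report wording, plus a little computing if the bootstrap is used. Section 4.2.1 dates DCO1 to 15 January 2019, and section 4.2.2 makes the later investigator-assessed PFS analysis descriptive. The change is therefore to interpretation; the planned test stays as it is.
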